Treatment With Cannabis Oil Containing Canabidiol (CBD) Only or 20:1 CBD:THC vs. Placebo of Persons Diagnosed With ADHD After Failure of Conventional Treatment

Date: 16/08/21 Protocol number: 232-19-ASF

Version 4

Background

ADHD is the most frequent neuro-developmental disorder in childhood affecting around 8% of children and continues into adolescence and adulthood for some 70% of them. In some cases, ADHD appears in adulthood.

There are 3 subtypes for this disorder:

Mainly inattentive, mainly hyperactive-impulsive and combined type.

Indicated drug treatments for ADHD fall into 2 categories: stimulants (such as

methylphenidate and amphetamines) and non-stimulants (such as atomoxetine, guanfacine and clonidine) but some patients cannot tolerate their side effects (decreased appetite and weight, insomnia, irritability, headache, fatigue, etc) or serious side effects like psychosis onset and CV complications or find them non effective in some 50% of the cases.

In the last decade, medical cannabis products have been researched as possible treatment for neurological and mental diseases such as: PTD, ASD, epilepsy, FM and more.

Data on the effects of cannabidiol rich cannabis extract use for ADHD seems promising but is still limited.

The aim of this study is to investigate if oral cannabinoids given to adults with ADHD affect the symptoms of the disorder. At the same time, side effects and DDI will be assessed.

In this trial, 3 different types of cannabis oil will be compared to a placebo drug.

Participants will be randomized to any of the 4 arms.

Objectives

Primary

To assess the efficacy of the cannabis oil treatment containing different concentrations of CBD, THC, CBDV, CBG as per TOVA and Conners test results.

Secondary

To assess side effects of cannabis treatments and to compare them with those of conventional drugs prescribed for ADHD.

To assess the quality of life of participants with ADHD treated with the different cannabis oils.

Methods

Participants will undergo a prescreening interview (phone and mail) which includes: inclusion/exclusion criteria, medical history and concomitant medications, previous treatments for ADHD. After assuring the eligibility to the study, the will be invited to take part in the study.

Each participant will attend three visits in the clinic and will be contacted by phone twice.

Visit 1: randomization, day 1

Actions and procedures:

- Consent process, including signing ICF
- inclusion/exclusion criteria

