- -Participants using cannabis or products containing cannabinoids, including medical cannabis.

Sample size calculation

In order to detect differences at p=0.05 with 80 % power, 53 participants in each arm (total of 212 participants) will be needed. With an estimation of 15% drop-out, 244 participants will be recruited.

Statistical analysis plan

Paired T-tests to assess longitudinal changes in scores before and under treatment will be performed for each participant.

In addition, results from the 4 arms will be compared.

Trial products

If possible the trial drugs will be dispensed with a syringe instead of a dropper. Dosage will stay identical and will be measured by volume.

table 1. Max. daily dose in mg of each cannabinoid in the different trial products

arm	CBG	CBDV	THC	CBD
	(mg/day)	(mg/day)	(mg/day)	(mg/day)
Placebo	0	0	0	0
Arm1	0	27	9	171
Arm 2	171	0	4.5	0
Arm 3	171	27	9	171

In arm 3 that contains higher dosages, a person weighing 45 kg (minimum for participating) and receiving the max dosage of 60 drops will get 3.8 mg/kg/day CBD and 0.2 mg/kg/day THC.

In special cases (for ex. extreme BMI) investigator will consider changing the dosage program from the standard in the trial in order to adapt them better to the participant.

Participants will keep a diary (hard copy or electronic) and fill in actual treatment ingestion.

In any case, daily dose will not exceed 400 mg CBD and 20 mg THC.

Placebo will have same package, color and taste as trial product.

Treatment cessation

Treatment cessation because of early termination will be done as described in dose regimen or as per researcher decision.

Bibliography

Coghill, D.R et al. Long-Term Safety and Efficacy of Lisdexamfetamine Dimesylate in Children and Adolescents with ADHD: A Phase IV, 2-Year, Open-Label Study in Europe. CNS Drugs 31, 625–638 (2017). https://doi.org/10.1007/s40263-017-0443-y

Cooper RE et al. Cannabinoids in attention-deficit/hyperactivity disorder: A randomised-controlled trial. European Neuropsychopharmacology Volume 27, Issue 8, August 2017

Devinsky, O et al. 2014. Cannabidiol: pharmacology and potential therapeutic role in epilepsy and other neuropsychiatric disorders. Epilepsia 55, 791–802. http://dx.doi.org/10.1111/epi.12631

Stone NL et al. Protective Effects of Cannabidivarin and Cannabigerol on Cells of the Blood–Brain Barrier Under Ischemic Conditions. Cannabis and Cannabinoid ResearchVolume 6, Number 4, 2021 Mary Ann Liebert, Inc.DOI: 10.1089/can.2020.0159

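### The only named efficacy test uses just those participants with a Visit 2 score, and the plan does not define follow-up after early stopping, the arm comparison or the handling of missing scores

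*Combined protocol and SAP*

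**What the plan says.** All references are to the combined protocol and SAP.

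- **Statistical analysis plan.** "Paired T-tests to assess longitudinal changes in scores before and under treatment will be performed for each participant". One further sentence adds a comparison across the four arms. It gives no test, model, analysis set, missing-data rule or sensitivity analysis.
- **Sample size calculation.** "In order to detect differences at p=0.05 with 80 % power, 53 participants in each arm (total of 212 participants) will be needed". Then: "With an estimation of 15% drop-out, 244 participants will be recruited". Drop-out appears nowhere else in the plan.
- **Objectives.** Efficacy is judged "as per TOVA and Conners test results".
- **Methods, visit list.** TOVA is done at Visit 1 and at Visit 2 (day 26 ± 2). Questionnaires, including behaviour, are completed at Visits 1, 2 and 3. The day 14 contact collects adverse events, medication changes and a blinding questionnaire, but no efficacy score. Visit 3 is at day 42; under Dose regimen, treatment ends on day 32.
- **Treatment cessation.** "Treatment cessation because of early termination will be done as described in dose regimen or as per researcher decision". This covers how dosing ends. It does not mention assessments or later visits.

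**The concern.** A paired test needs both scores from the same person, so anyone without a Visit 2 score falls out of the named analysis. TOVA has no other post-baseline reading. The behaviour questionnaires are repeated at day 42, but that is ten days after the last dose and cannot stand in for a score under treatment.

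Drop-out may well be related to treatment. Placebo contains no cannabinoid, the oil volume is raised in steps up to the period around Visit 2, and side effects are a stated secondary objective. If the chance of leaving, or the outcome of those who leave, differs between arms, a comparison of those who remain is no longer the comparison that randomisation set up. Recruiting more people does not repair that.

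The paired tests also cannot carry the efficacy claim, because a before-after change within an arm includes whatever would have happened on placebo. The result that matters is the arm contrast, and that is the part left undefined.

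**Working it through.** **1. The plan's recruitment figure.** Inputs from Sample size calculation: 53 per arm, four arms, 15% drop-out.
- 4 × 53 = 212.
- 212 × 1.15 = 243.8, rounded up to 244 (61 per arm). The figure is reproduced.
- Dividing instead, 212 / 0.85 = 249.4, or 250. The gap is small and is not the issue here.

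**2. How many could lack a Visit 2 score.**
- 0.15 × 244 = 36.6, about 37. This is an upper figure for the stated rate, because the plan gives no timing and some may leave after Visit 2.
- 244 − 36.6 = 207.4, or 51.85 per arm.

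**3. Lost numbers are a minor matter.** The plan states no effect size or SD. Assuming a two-sided, two-sample comparison, 53 per arm at 80% power corresponds to (1.960 + 0.842) × √(2/53) = 0.544 SD. At 51.85 per arm, power for that difference is 79.1%. For a paired test the same 53 would correspond to (1.960 + 0.842) / √53 = 0.385 SD, so percentages of 0.544 depend on the two-sample assumption.

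**4. Possible bias in the arm contrast.** Let p be the proportion without a Visit 2 score and g the amount, in SD, by which their outcome is worse than that of completers. The completer mean in an arm exceeds the mean of all randomised by p × g. The bias in oil minus placebo is therefore

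p(oil) × g(oil) − p(placebo) × g(placebo).

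The documents give no value of p by arm and no value of g. The cases below are assumptions, each averaging 15% over three oil arms and one placebo arm of equal size.

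| Oil p | Placebo p | Overall | g | Bias |
|---|---|---|---|---|
| 15% | 15% | 15% | equal in both | 0 |
| 18% | 6% | (3 × 18 + 6)/4 = 15% | 0.25 in both | 0.12 × 0.25 = 0.03 SD |
| 18% | 6% | 15% | 1.0 in both | 0.12 × 1.0 = 0.12 SD |
| 15% | 15% | 15% | 0.25 oil, 1.0 placebo | 0.0375 − 0.15 = −0.11 SD |

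A positive sign favours the oil. The last row shows that the sign can reverse when leavers on placebo do worse.

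**5. What the 18% versus 6% case would mean.** The bias is 0.03/0.544 = 6% to 0.12/0.544 = 22% of the back-solved difference. With no true effect, the standard error is √(1/(61 × 0.82) + 1/(61 × 0.94)) = 0.193 SD. The two-sided false-positive rate then rises from 5% to between 5.3% and 9.5%.

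**The case against.** The strongest reply is that the plan is brief rather than wrong. Methods has every participant attending three clinic visits, and willingness to attend them all is an inclusion criterion. Neither statement is limited to people still taking the oil. The cessation sentence is about dosing, not about leaving the study. Someone who stops the oil but comes to Visit 2 has both scores and stays in the paired test. The arm comparison, having no stated method, is not committed to completers. The bias figures rest on assumed inputs.

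Much of this stands, and it rules out stronger readings:
- A reader might infer that nothing is collected from early stoppers. The text does not say so; it leaves open whether they attend Visit 2.
- A reader might infer that the bias favours the oils. That needs more, or worse, leavers in the oil arms, and the plan gives neither rates nor reasons by arm.
- A reader might take about 37 losses before Visit 2 as planned. The 15% has no timing.

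The reply does not remove the gap. Whatever stoppers do, anyone without a Visit 2 score is outside the only named test, and that test does not compare arms. The single provision for drop-out is a larger recruitment number. With no rule stated, a comparison of the available scores is the likely default.

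**Conclusion.** The point holds as a gap in the analysis and follow-up plan. The paired tests certainly exclude anyone without a Visit 2 score. For the arm comparison, restriction to participants with scores is the probable default, not a stated choice.

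Up to about 37 of 244 could be affected, if all of the 15% drop-out falls before Visit 2. The loss of power is slight. The issue is possible bias of unknown sign: zero with equal drop-out and equal deficit, and 0.03 to 0.12 SD in the 18% versus 6% illustration. Those sizes show what is plausible under stated assumptions; they are not estimates for this trial. The plan should be changed, because scores not collected at Visit 2 cannot be recovered later and a missing-data rule chosen after unblinding would carry little weight.

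**What to change.** 1. State that participants who stop the oil early remain in the visit schedule and complete TOVA and questionnaires at Visit 2.
2. Make the primary analysis an ANCOVA of Visit 2 scores, adjusted for baseline, comparing each oil with placebo, with all randomised participants kept in their assigned arm whether or not they were still taking the oil. State that scores still missing are assumed missing at random given arm and baseline. Treat the within-arm paired t-tests as supportive.
3. Add one sensitivity analysis for missing Visit 2 scores, such as imputing the placebo mean in the oil arms or applying a worsening delta. Multiple imputation for the primary analysis is optional: with a single post-baseline score it adds little to the ANCOVA.

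The cost is a little more analysis and some effort to bring people back to visits that are already scheduled. The estimate may be smaller than one from completers. For example, assume a 0.544 SD effect that is lost in the 15% who stop. The expected difference is then 0.544 × 0.85 = 0.463 SD, and power with all 61 per arm analysed is about 72%. The sponsor should know this when setting the sample size.

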- Review of medical history and concomitant medications
- TOVA test
- Vital signs and physical examination
- Urine and blood test
- Questionnaires filling (eat, sleep, behavior)
- Randomization
- Drug dispense and instructions for use

Follow up: day $14 (\pm 3 \text{ days})$

• Adverse events, change in concomitant medications, blinding questionnaire

Visit 2: end of treatment, day 26 (± 2 days)

Actions and procedures:

- Adverse events, change in concomitant medications
- TOVA test
- Vital signs and physical examination
- Urine and blood test
- Questionnaires filling (eat, sleep, behavior)

Visit 3: follow up, day 42 (±2 days)

- Adverse events, change in concomitant medications
- Questionnaires filling (eat, sleep, behavior)

• Return of study drug

Dose regimen

Days 1-2: 10 drops/day (total 0.3 ml/day)*

Days 3-7: 20 drops/day (total 0.6 ml/day)

Days 8-21: 40 drops/day (total 1.2 ml/day)

Days 22-28: 60 drops/day (total 1.8 ml/day)

After day 28, dose will be tapered: 40 drops at day 29, 20 drops at day 30, 10 drops at days 31-32. Day 32 will be the last day of treatment.

*The volume of one drop is approx.0.03 ml.

Main inclusion criteria:

- Participants aged at least 18 years old diagnosed with ADHD by DSM
- -Participants with a smaller than 0 TOVA score or with a greater than 0 score that as per investigator opinion suffer from ADHD
- -Participants who experienced treatment failure with more than one ADHD conventional drug
- Participants willing to attend all the visits in the trial.

Main exclusion criteria:

- Participants who were treated with benzodiazepines or antihistamines in the week that preceded the trial start.
- -Participants suffering from neurologic or psychiatric diseases
- -Participants suffering from malignant diseases
- -Participants suffering from syndromes or metabolic diseases
- -Participants with significant clinical diagnosis that can damage the trial unfolding. The investigator may include them after the end of the situation which prevented their previous inclusion.
- -Participants breastfeeding, pregnant or not willing to use contraceptives.
- -Participants that will not follow the protocol as per investigator opinion.
- -Participants who weight less than 45 kg or more than 120kg or with BMI greater than 30

- -Participants participating in another clinical trial which includes drug treatment
- -Participants receiving any treatment for ADHD
- -Participants using drugs

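### The only named test is a before-and-after paired t-test that makes no use of placebo; the four-arm comparison has no method and is not declared primary

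*Combined protocol and SAP*

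**What the plan says.** The Background sets the question: "In this trial, 3 different types of cannabis oil will be compared to a placebo drug". The title also frames the study as a comparison with placebo. The primary objective does not mention placebo: "To assess the efficacy of the cannabis oil treatment containing different concentrations of CBD, THC, CBDV, CBG as per TOVA and Conners test results".

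The Statistical analysis plan is two sentences. The first is "Paired T-tests to assess longitudinal changes in scores before and under treatment will be performed for each participant". The second is "In addition, results from the 4 arms will be compared". Neither is called primary. The second gives no test, model, contrast, endpoint, time point or multiplicity rule.

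The Sample size calculation does not say which analysis it serves: "In order to detect differences at p=0.05 with 80 % power, 53 participants in each arm (total of 212 participants) will be needed". It states no effect size, SD or test. The visit schedule lists TOVA at Visit 1 (before treatment) and at Visit 2 (day 26), and nowhere else.

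**The concern.** A paired t-test asks whether scores moved from their own baseline. In this trial they may move without any drug effect. TOVA is repeated, so practice can help; participants may expect benefit; and entry partly depends on a TOVA score below 0. If the Visit 1 score serves both for entry and as baseline, some improvement is expected from regression to the mean. Randomised placebo is there to remove such change, but only if each oil is contrasted with it directly.

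The two sentences of the plan can be read in two ways:

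- **(a)** Each participant's change is calculated and the changes are compared across arms. This uses placebo properly.
- **(b)** A paired test is run in each arm and the results are set side by side. This is not a valid comparison with placebo, because significant in one arm and not in another does not show that the arms differ.

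If the choice is left open, it can be made after the data are seen, and under (b) a non-specific change could be reported as efficacy.

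**Working it through.** **1. Can the paired test be run as written?** One participant has one TOVA score before treatment and one under treatment: one difference, so n − 1 = 0 degrees of freedom. The test cannot be done per participant. It presumably means across participants within an arm.

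**2. Does the sample size show which analysis was meant?** The totals follow: 4 × 53 = 212, and 212 × 1.15 = 243.8, or 244. The 53 itself cannot be reproduced, since no effect size is given. Solving backwards at 80% power and two-sided 0.05 (sidedness is not stated):

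- Between two arms: d = (1.960 + 0.842) × √(2/53) = 0.544; 0.549 with the t distribution.
- Within one arm: dz = (1.960 + 0.842)/√53 = 0.385; 0.392 with the t distribution.

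Both are plausible targets, so 53 per arm does not settle it. If it was sized for the within-arm test, a between-arm difference of 0.385 SD has only 51% power and would need 106 per arm.

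**3. What does each reading do when no oil works?** Assumptions, none of them from the documents: 53 analysed per arm, no drug effect, the same mean shift s (in SDs of the score) in all four arms, and test-retest correlation r. Then:

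- Standardised change: dz = s/√(2(1 − r)).
- p = two-sided power of the paired t-test at n = 53 (noncentral t).
- A given oil significant and placebo not: p(1 − p).
- At least one of three oils significant and placebo not: [1 − (1 − p)³](1 − p).

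| Shift | Result | r = 0.5 | r = 0.7 | r = 0.8 |
|---|---|---|---|---|
| 0.1 SD | one arm's paired test significant | 11% | 15% | 20% |
| 0.1 SD | any oil significant, placebo not | 26% | 33% | 40% |
| 0.2 SD | one arm's paired test significant | 30% | 45% | 62% |
| 0.2 SD | given oil significant, placebo not | 21% | 25% | 24% |
| 0.2 SD | any oil significant, placebo not | 46% | 46% | 36% |
| 0.3 SD | one arm's paired test significant | 57% | 79% | 92% |
| 0.3 SD | any oil significant, placebo not | 39% | 21% | 8% |

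Example: s = 0.2 and r = 0.5 give dz = 0.2 and p = 0.298, so p(1 − p) = 0.209 and [1 − 0.702³] × 0.702 = 0.459. The side-by-side rate falls at the largest shift because placebo is then usually significant too.

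With no shift, p = 0.05 and the any-of-three rate is (1 − 0.95³) × 0.95 = 13.5%. That part is multiplicity; the excess over it is the cost of not contrasting with placebo.

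**4. What does a direct contrast do?** In a simulation of four arms of 53 (20,000 trials, no drug effect, shifts of 0.2 and 0.3 SD), ANCOVA contrasts with placebo rejected in 4.8–5.1% per oil and 12.2–12.8% for any of three. Change-score contrasts gave 4.8–5.2% and 12.3–13.0%. A shift common to all arms cancels.

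**5. Power of the two valid methods** at d = 0.549 in raw-score SDs, 53 per arm. The effective difference is d/√(1 − r²) for ANCOVA (207 df) and d/√(2(1 − r)) for the change score (208 df).

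| Method | r = 0.3 | r = 0.5 | r = 0.7 |
|---|---|---|---|
| ANCOVA, α = 0.05 | 84% | 90% | 98% |
| Change score, α = 0.05 | 66% | 80% | 95% |
| ANCOVA, α = 0.05/3 | 71% | 80% | 94% |

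Without baseline adjustment, power at α = 0.05/3 is 66%.

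**The case against.** The strongest reply is that the placebo comparison is not absent. The Background states it and the analysis plan promises it. Because a paired test cannot be run on a single participant, the wording may simply mean that each person's change is calculated and the arms then compared, which is reading (a). Under that reading the bias does not arise. This stands in part: the risk is conditional, and the fault is not that a wrong test was declared primary. But reading (b) stays open, and nothing elsewhere in the document names a between-arm method or gives it primary status.

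The percentages rest on assumed shifts and correlations, and the documents show no practice effect on TOVA. That is true, and they illustrate a mechanism only. A lower correlation gives lower paired-test rates: at r = 0.3 and 0.2 SD, p is 23% and a given oil passes with placebo not in 17.5%. Still, any of three passes in [1 − 0.773³] × 0.773 = 42%, so the conclusion does not move.

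Finally, preferring ANCOVA to a change score is a matter of efficiency, and its size depends on the unit of the 0.55 SD. If that is an SD of the change score, change-score power is 80% at every r, against 94%, 90% and 86% for ANCOVA at r = 0.3, 0.5 and 0.7. ANCOVA is ahead in either unit, but either method removes the bias.

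**Conclusion.** The concern holds and should be fixed before the data are unblinded. The one test the plan specifies cannot answer the placebo question, and the comparison that can answer it has neither a method nor primary status. That much rests on the text alone.

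The size is conditional on efficacy being judged by paired tests. Under the stated assumptions, a shift of 0.1 to 0.3 SD common to all arms makes an ineffective oil's paired test significant between 11% and 92% of the time. Setting results side by side gives at least one false claim in 8% to 46% of trials, against 13.5% with no shift. Direct contrasts stay at 5% per oil whatever the shift; their 12–13% for any of three is a separate multiplicity matter.

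**What to change.** State in the Statistical analysis plan that efficacy is decided by the between-arm comparison, and name the method. The preferred choice is an ANCOVA of the Visit 2 TOVA score with arm as factor and the Visit 1 TOVA score as covariate. Analyse participants in their randomised arm, report per arm how many lack a Visit 2 score, and give each oil minus placebo with a 95% confidence interval. A between-arm comparison of change scores is valid but generally less powerful.

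Keep the paired t-tests only as within-arm description, run per arm, and say that they are not evidence of efficacy. Apply the same model to Conners if it is collected at both visits. The schedule mentions only questionnaires on eating, sleep and behaviour, so whether Conners is among them cannot be told. How TOVA and Conners share primary status is a separate decision.

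The cost is SAP wording and slightly more analysis work: no new visits and no new TOVA data. Conners may need added collection. If the three placebo contrasts are adjusted for multiplicity, the power statement for 53 per arm must be redone. With Bonferroni at the back-solved 0.55 SD, it is about 66% without baseline adjustment and 71%, 80% or 94% with ANCOVA at r = 0.3, 0.5 or 0.7.

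### Does a dose ceiling that names only CBD and THC leave CBG and CBDV without a limit?

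*Combined protocol and SAP*

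**What the plan says.** All the relevant text on limits is in the Trial products section of the combined protocol and SAP, read with Dose regimen.

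- Table 1 is headed "Max. daily dose in mg of each cannabinoid in the different trial products". It lists 171 mg CBD, 9 mg THC and 27 mg CBDV for Arm 1; 171 mg CBG and 4.5 mg THC for Arm 2; and 171 mg each of CBD and CBG, 27 mg CBDV and 9 mg THC for Arm 3.
- A worked example takes the lightest eligible participant, "In arm 3 that contains higher dosages, a person weighing 45 kg (minimum for participating"; that person, "receiving the max dosage of 60 drops will get 3.8 mg/kg/day CBD and 0.2 mg/kg/day THC".
- In special cases, with extreme BMI as the only example, the "investigator will consider changing the dosage program from the standard in the trial in order to adapt them better to the participant". Neither the direction nor the size of such a change is given.
- The ceiling follows: "In any case, daily dose will not exceed 400 mg CBD and 20 mg THC". CBG and CBDV are not mentioned in it.
- On delivery by syringe instead of dropper: "Dosage will stay identical and will be measured by volume". On masking: "Placebo will have same package, color and taste as trial product". The day 14 contact includes "Adverse events, change in concomitant medications, blinding questionnaire".

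Dose regimen rises in steps from 0.3 to 1.8 ml per day and then tapers. It never exceeds 60 drops.

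**The concern.** Two sets of numbers look like the limit. Table 1 and the worked example point to 60 drops. The ceiling is more than twice as high for CBD and THC and is worded as absolute. If special-case changes may go up to the ceiling, the Table 1 figures and the 3.8 and 0.2 mg/kg are not true maxima for those participants.

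The ceiling also omits two of the four cannabinoids named in the primary objective. Arm 2 has no CBD, so the CBD limit has no effect there, and its CBG is held down only through a small THC content. A safety reader could fairly ask what maximum exposure is being approved, in whom, and for which substances.

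A side issue is that the title describes a CBD-only oil and a 20:1 CBD:THC oil, whereas every active arm in Table 1 contains THC and Arm 2 contains no CBD.

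**Working it through.** **Inputs.** Table 1 doses as listed above; 60 drops per day at about 0.03 ml per drop (Dose regimen); weight 45 to 120 kg and BMI not above 30 (Main exclusion criteria); ceiling 400 mg CBD and 20 mg THC (Trial products). Assumption: each oil has a fixed composition, so all its ingredients scale with volume.

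**1. The plan's own figures.** 60 × 0.03 = 1.8 ml. At 45 kg, 171/45 = 3.8 mg/kg CBD and 9/45 = 0.2 mg/kg THC. Both reproduce exactly.

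**2. Is there a contradiction?** The highest CBD dose in Table 1 is 171 mg, below 400. The highest THC dose is 9 mg, below 20. All arms satisfy both statements at once. Under the written regimen CBG is at most 171 mg and CBDV at most 27 mg per day.

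**3. What would the ceiling alone allow?** Concentrations are Table 1 divided by 1.8 ml: CBD and CBG 171/1.8 = 95 mg/ml; CBDV 27/1.8 = 15 mg/ml; THC 9/1.8 = 5 mg/ml in Arms 1 and 3, and 4.5/1.8 = 2.5 mg/ml in Arm 2.

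| | Volume at ceiling | Multiple of 1.8 ml | Content |
|---|---|---|---|
| Arms 1 and 3 | min(400/95 = 4.21; 20/5 = 4.0) = 4.0 ml | 2.22 | CBD 380, THC 20, CBDV 60 mg; CBG 380 mg in Arm 3 |
| Arm 2 taken alone | 20/2.5 = 8.0 ml | 4.44 | CBG 8.0 × 95 = 760 mg, THC 20 mg |

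**4. Can the Arm 2 figure arise without knowing the arm?** At 8.0 ml, Arms 1 and 3 would carry 8.0 × 5 = 40 mg THC, twice the ceiling. Someone dosing by volume without knowing the arm can be sure of respecting the ceiling only up to 4.0 ml. At 4.0 ml Arm 2 contains 4.0 × 95 = 380 mg CBG and 4.0 × 2.5 = 10 mg THC. Arms 2 and 3 then have the same CBG.

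**5. Per kilogram at 4.0 ml.** For CBD in Arms 1 and 3, and equally for CBG in Arms 2 and 3: 380/45 = 8.4 mg/kg and 380/120 = 3.2 mg/kg. The dose falls to the worked 3.8 mg/kg at 380/3.8 = 100 kg. For THC in Arms 1 and 3 the same weight results: 20/0.2 = 100 kg. So if 4.0 ml were ever used, the worked figures would be exceeded below 100 kg. These are arithmetic outer limits; the document describes no dosing path that leads to them.

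**6. Title.** The CBD:THC ratio in Arms 1 and 3 is 171/9 = 19, close to the titled 20:1. None of the three active arms is CBD alone. The Background (three oils against placebo) and the primary objective (CBD, THC, CBDV and CBG) agree with Table 1.

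**The case for a change.** The strongest argument for a change is a dilemma. If special-case changes may exceed 60 drops, Table 1 is mislabelled for those participants. If they may not, the ceiling does no work, because every Table 1 value already lies below it. On either reading one sentence is not doing what it appears to do. Even on the masked reading, CBG could reach 2.22 times its Table 1 value with no limit naming it, and no CBG or CBDV figure per kilogram is given.

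Part of this stands. The text does not say how the ceiling, the 60-drop maximum and the special-case clause fit together, and the ceiling omits CBG and CBDV. If doses above 60 drops were meant, the Table 1 and worked values would not be maxima.

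The rest does not carry the weight put on it. A redundant outer bound is not an error. Table 1 sets CBG and CBDV maxima in so many figures, and no sentence expressly authorises more than 60 drops. The 760 mg, 4.44-fold and 16.9 mg/kg (760/45) figures require a prescriber who knows the arm, whereas the matched placebo and the blinding questionnaire point to masking. The worked example already uses the lowest eligible weight, which gives the highest exposure per kilogram on the standard regimen. The remaining per-kilogram values are simple divisions of Table 1.

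**Conclusion.** The concern is accurate on the wording but does not call for a change. It is missing detail about how existing limits relate. Following the written regimen keeps every arm within Table 1 for all four cannabinoids, and no two figures conflict. The planned analysis (paired before-and-after comparisons and a comparison of the four arms) makes no use of the ceiling, so results and conclusions are the same whichever way the sentence is read. Participants record actual intake in a diary, so any special-case departure would be visible to the analyst.

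The size of what is left open is at most 2.22 times the Table 1 doses (4.0 ml against 1.8 ml), in special cases only, and only if such changes may go above 60 drops. This rests on two assumptions: fixed composition of each oil, and dosing by volume without knowledge of the arm. The document does not state who is masked. If the prescriber knew the arm, the arithmetic limit for Arm 2 would be 4.44 times.

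How the maximum, the special-case clause and the ceiling are to be read together, including for CBG and CBDV, is for the sponsor's medical lead to reconcile. This review takes no position on which limit should govern. The title's mention of a CBD-only oil is a clerical slip, since the Background, the primary objective and Table 1 agree on what is being tested.
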